### 7.3. Interventions

#### 7.3.1. Methylnaltrexone dosage and treatment duration

To ensure standardization of the protocol, patients with AP will be treated with methylnaltrexone or placebo intravenously for the first 5 days of admission and assessments of endpoints will be done at fixed time points during this period. The dosage will be weight adjusted. Thus, 0.15 mg/kg methylnaltrexone or a corresponding volume of matching placebo (Ringer's lactate) will be dissolved in 1000 mL Ringer's lactate solution and given as a continues infusion over 24 hours using an infusion pump. In accordance with the summary of product characteristics for methylnaltrexone, a 50 % dose reduction will be made for patients with an eGFR below 30 ml/min/1,73m^2. the continuous infusion of study medication will be started no later than 24 hours after preparation. This will be ensured by keeping detailed record on the time of preparation

as well as time of infusion start. As methylnaltrexone is sensitive to light, the solution will be kept protected from light from the time of preparation until the time of infusion start. Two persons trained in the protocol and delegated to do so, will prepare the solution of study medication together. This will be done with one person assisting virtually in exceptional cases.

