#### 7.3.2. Discontinuation or withdrawal from the study

If the treatment-responsible doctor should at any point during the study assess that the patient suffers from end-stage renal impairment requiring dialysis, the treatment with methylnaltrexone will be discontinued.

Furthermore, a participant should be withdrawn from trial, if at any time:

- It is the wish of the participant for any reason
- The investigator judges it necessary due to medical reasons

If a participant is withdrawn from the trial, the investigator should always ensure that:

- Case report form (CRF) end of trial pages should be completed for withdrawn participants
- Any serious adverse events still ongoing after ended trial will be followed until the event has been resolved or the investigator assesses them as chronic or stable

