### 7.4.2. Secondary endpoints

- Difference in daily **PASS scores** between subgroups
- Difference in daily assessments of circulating **pro- and anti-inflammatory markers** (including CRP, IL-6, IL-8, IL-18, TNF- $\alpha$  and CD163) as well as **intestinal barrier markers** between subgroups
- Difference in **intestinal permeability** between subgroups measured from 48 to 72 hours after randomization using the oral polyethylene glycol 400/4000 test
- Difference in **intestinal motility** assessed by means of gut/colon transit using a CT-based radiopaque marker method on day 5 (+/- 1 day) between subgroups
- Difference in **pancreatic complications** (e.g. edema, fluid collections and necrosis) assessed and quantified with contrast-enhanced CT on day 5 (+/- 1 day) after randomization (20)
- Difference between subgroups in the following **clinical outcome parameters**: pain intensity and gut function (assessed by questionnaires), quantification of analgesics (separated into opioids and non-opioids), need for nutritional support, disease severity, invasive treatments, intensive care and hospital stay, as well as mortality during total hospitalization
- Difference in **health resource utilization** during hospitalization between subgroups

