- ≥ 48 h of treatment, but discharge before day 5: Participant will be lost to follow-up on the following outcomes: daily PASS scores, blood samples, vital signs, quantification of need for analgesics, nutritional support, intravenous fluid resuscitation and antibiotics, and data will be analyzed using the Last-Observation-Carried-Forward method (see section 9.3.). The participant will be asked to complete questionnaires at home and they will be offered a follow-up CT scan in an outpatient setting on day 5 (+/- 1 day). Furthermore, they will be invited to participate in the 14-day follow-up and readmission rates as well as mortality will be registered retrospectively.

Randomization	Methylnaltrexone or placebo (0.15 mg/kg/day)				End of study	Follow-up
Baseline	24±2 hours	48±2 hours	72±2 hours	96±2 hours	120±2 hours	14±2 days
PASS	PASS	PASS	PASS	PASS	PASS	PASS
Clinical outcome	Clinical outcome	Clinical outcome	Clinical outcome	Clinical outcome	Clinical outcome	Clinical outcome
Blood samples	Blood samples	Blood samples	Blood samples	Blood samples	Blood samples	Blood samples
		Intestinal permeability		Intestinal transit time		

Computed tomography				Computed tomography	Health resource utilization
---------------------	--	--	--	---------------------	-----------------------------

**Table 1:** Participant timeline. PASS; pancreatitis activity scoring system.

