### 9.3. Statistical methods

A repeated measures linear mixed effects model will be used for the primary analysis and will include terms for treatment group, assessment time point (day after randomization), and the interaction of treatment with assessment time point. Summary statistics and trend curves of PASS scores will be provided for the individual time points, and the difference in PASS scores between groups 48 hours after randomization is considered the primary efficacy parameter. Subgroup and covariate analyses will be performed if applicable and in case differences in patient subgroups deemed clinically relevant are evident. The primary analysis will be by intention to treat and in case of early hospital discharge or other reasons for missing values, the Last-Observation-Carried-Forward method will be employed. Trends in PASS and other secondary endpoints assessed consequently during the treatment period (biochemical tests and clinical outcome parameters) are analyzed using linear random-effects models and results presented as fitted trend curves. Outcomes assessed at single time points (baseline characteristics, CT features and gut permeability) are compared using Student's t-test or non-parametric analysis for continues data as appropriate. Binary outcomes will be analyzed using Fisher's exact test. All secondary endpoints will be analyzed by per-protocol.

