2.3. Exploratory Objectives

The exploratory objectives are to examine the effects of methylnaltrexone treatment on the immune system, the gastrointestinal tract, and the pancreas. This is to examine whether treatment with methylnaltrexone may reverse potentially opioid-induced changes to these organs.

The exploratory outcomes are listed below:

- Difference between treatment groups on daily levels of circulating pro- and anti-inflammatory blood markers during treatment and at 14-day follow-up
- Difference between treatment groups in intestinal permeability measured based on the polyethylene glycol (PEG) 400/4000 test (16). Following ingestion of a PEG solution containing 5 g PEG 400 and 5 g PEG 4000 dissolved in 100 ml water, patients will have their urine collected for 24 hours. The small size molecules (PEG 400) traverse the intestinal barrier freely, independent of barrier function loss, whereas the large size molecules (PEG 4000) only cross the intestinal wall and becomes detectable in urine in

case of intestinal barrier function loss. Based on the ratio between the two molecules measured in the urine, we can approximate the intestinal permeability

- Difference between treatment groups on gut transit time assessed using a CT-based radiopaque marker method, where the patients are asked to ingest a capsule containing radiopaque markers 48 hours prior to a CT scan. Based on the location of the markers on the CT-scan, the transit time can be approximated
- Difference between groups on the prevalence of pancreatic complications assessed and quantified using a CT-scan according to the Atlanta criteria (10)

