2.5. Specification of endpoints

The primary outcome at the primary endpoint will be analyzed by intention-to-treat (ITT), whereas the secondary endpoints will be per-protocol (PP) analyses. Several factors such as treatment effect of methylnaltrexone and possible side-effects (17) may lead to an uneven distribution between excluded patients in the treatment groups (e.g. if methylnaltrexone patients are discharged earlier or discontinue treatment due to side effects). The ITT-analysis will protect against the potential bias of excluding patients unevenly according to which treatment they received. Only if the participant is randomized but never receives treatment, will they be excluded from the ITT-analysis.

The PP-analysis aims to uncover the treatment effect under ideal conditions in terms of treatment duration and follow-up. Furthermore, the PP-analysis is expected to provide mechanistic insights into the role of opioids and opioid antagonism in acute pancreatitis. Participants are included in the PP-analysis, when:

1. > 75 % of the study drug has been given
2. No major protocol deviations have been recorded

The trial is designed as a superiority trial, and we expect to see an effect of treatment after 48 hours of treatment – which is the explanation for choice of primary endpoint. Thus, we expect that the group allocated to the methylnaltrexone treatment, compared to the usual care group, will have:

1. Reduced disease severity (lower PASS-scores, lower prevalence of severe disease)
2. Improved clinical outcomes (lower pain scores, shorter admission lengths, reduced mortality, inflammatory cytokines/intestinal permeability/transit times closer to normal range, reduced prevalence of pancreatic complications)

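### Day-5 CT complications are assigned to a per-protocol set that may drop early-discharged patients who are offered the scan, and no analysis of all available scans is planned

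*Protocol*

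**What the plan says.** **Endpoint and analysis set.** Protocol 7.4.2 makes pancreatic complications a secondary endpoint, "assessed and quantified with contrast-enhanced CT on day 5 (+/- 1 day) after randomization (20". Protocol 9.3 then says "All secondary endpoints will be analyzed by per-protocol". SAP 2.5 assigns intention to treat to the primary outcome, "whereas the secondary endpoints will be per-protocol (PP) analyses".

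**Definition of per protocol.** SAP 2.5 sets two conditions: "> 75 % of the study drug has been given", and no major protocol deviation on record. It does not say what the 75% is a percentage of. The planned course is 5 days; each daily dose is "given as a continues infusion over 24 hours using an infusion pump" (Protocol 7.3.1).

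**Early discharge.** For patients with at least 48 h of treatment who leave before day 5, Protocol 7.5.1 says "they will be offered a follow-up CT scan in an outpatient setting on day 5 (+/- 1 day". SAP 6.3 repeats this in its Table 2, under the section title Major Protocol Deviations. It expects early discharge mostly through recovery and uses last observation carried forward (LOCF) for missing values.

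**Tier of the CT outcome in the SAP.** SAP 2.3 lists CT complications as exploratory. SAP 2.5 names no analysis set for exploratory outcomes.

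**Stated reasons.** SAP 2.5 wants the per-protocol analysis to show the effect under ideal treatment duration and follow-up, and to give mechanistic insight. The same section warns that exclusions could fall unevenly if methylnaltrexone patients go home earlier or stop because of side effects, and gives that as the reason for intention to treat on the primary outcome.

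**The concern.** Early discharge happens after randomization, and the SAP accepts that treatment may influence it. If early-discharged patients are removed from the CT comparison, the two remaining groups are no longer the randomized ones. SAP 2.5 predicts fewer pancreatic complications on drug. If the drug does speed recovery, more of its milder patients would leave the comparison, and a real benefit could be diluted or a false excess could appear.

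The opposite pull also exists. The per-protocol rule can remove sick patients, for example when "the patient suffers from end-stage renal impairment requiring dialysis, the treatment with methylnaltrexone will be discontinued" (Protocol 7.3.2), or when side effects or medical reasons stop the infusion. The direction is therefore not fixed.

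At stake is the interpretation of one imaging outcome and the use made of scans for which discharged patients are asked to return.

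**Working it through.** **The plan's own figure.** The only sample size given is for PASS at 48 h: n per group = 2 × (1.960 + 0.842)² × 40² / 25² = 2 × 7.85 × 2.56 = 40.2, rounded up to 41 and set at 45. It reproduces and is not in dispute. No figure is given for CT, so 45 per arm is used below.

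**Route (a): the dose criterion.** If the denominator is the planned course of 5 × 24 = 120 h, the cut is 0.75 × 120 = 90 h. Share of drug received = hours / 120:

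| Discharge at | Share | More than 75%? |
|---|---|---|
| 48 h | 40% | no |
| 72 h | 60% | no |
| 90 h | 75% | no |
| 96 h | 80% | yes |
| 108 h | 90% | yes |

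On this reading discharge from 48 h up to about 90 h excludes the patient, and later discharge passes. If the denominator is the drug planned up to discharge, this criterion excludes none of them for leaving early.

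**Route (b): the deviation criterion.** The early-discharge rules stand under the SAP 6.3 title Major Protocol Deviations. If early discharge is counted as such a deviation, every patient discharged before day 5 fails the second condition, whatever the 75% refers to.

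**Which set governs CT.** The SAP's list of secondary outcomes (2.2) omits CT, and its exploratory list (2.3) has no assigned set. The only sentence assigning a set to CT is the one in Protocol 9.3. Neither document adds an all-scans, intention-to-treat or sensitivity analysis of CT.

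**Illustration of size.** The documents give no early-discharge, complication or scan-uptake rates, so every input here is an assumption:

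- overall complication rate p = 0.40 in both arms (no drug effect)
- rate among early-discharged patients q = 0.10
- share excluded early e = 0.10 on placebo, and 0.20 or 0.30 on drug

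Rate in the analysed set = (p − e·q) / (1 − e). If all available scans are used and a fraction a of early-discharged patients accepts the outpatient scan, e becomes e(1 − a). Differences are taken before rounding.

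| Analysis | Placebo | Drug, e = 0.20 | Drug, e = 0.30 | False difference (points) |
|---|---|---|---|---|
| Per protocol, or all scans with a = 0 | 0.39/0.90 = 43.3% | 0.38/0.80 = 47.5% | 0.37/0.70 = 52.9% | +4.2 to +9.5 |
| All scans, a = 0.5 | 0.395/0.95 = 41.6% | 0.39/0.90 = 43.3% | 0.385/0.85 = 45.3% | +1.8 to +3.7 |
| All scans, a = 0.8 | 0.398/0.98 = 40.6% | 0.396/0.96 = 41.3% | 0.394/0.94 = 41.9% | +0.6 to +1.3 |

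Bias removed by using all scans: 4.2 − 1.8 = 2.4 to 9.5 − 3.7 = 5.8 points at 50% uptake; 3.5 to 8.2 points at 80%; none at zero uptake.

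Standard error of the per-protocol difference = √[p₁(1 − p₁)/n₁ + p₂(1 − p₂)/n₂], with n = 45 × 0.90 = 40.5 on placebo and 36 or 31.5 on drug: 11.4 or 11.8 points. At 50% uptake the removed part is 2.4/11.4 = 0.2 to 5.8/11.8 = 0.5 of a standard error.

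Scans brought back: 45 × (0.10 + 0.20) = 13.5 to 45 × (0.10 + 0.30) = 18 early-discharged patients, so about 7 to 9 scans at 50% uptake and 11 to 14 at 80%.

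**Offset.** Suppose a share s of drug patients is also excluded for severe illness, with an assumed complication rate of 0.80. The drug rate becomes (0.40 − 0.10e − 0.80s)/(1 − e − s). At s = 0.05 this is 0.34/0.75 = 45.3% or 0.33/0.65 = 50.8%, and the bias falls to +2.0 to +7.4. It reaches zero at s = 0.09 (e = 0.20) or s = 0.18 (e = 0.30). With equal early discharge, no drug effect and no such exclusions, it is zero throughout.

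**A second illustration, with a real benefit.** Assume complications in 10% of early-discharged and 50% of other patients in both arms, early discharge of 20% on placebo and 30% or 40% on drug, and full scan uptake. All scans give 0.2 × 10 + 0.8 × 50 = 42% on placebo against 38% or 34% on drug, a benefit of 4 to 8 points. Per protocol gives 50% against 50%.

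**The case against.** **The exclusion is not certain.** SAP 6.3 treats only patients with under 48 h of treatment as dropouts, keeps the others in follow-up, offers them CT and applies LOCF. One can read this as meaning that they stay in the secondary analyses. That is a fair reading, and the documents do not settle it. But the stated aim of ideal treatment duration leans towards the full-course denominator, and the title of SAP 6.3 points to the second route. LOCF does not resolve the matter: it fills missing values for patients in the set and does not return patients to it.

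**CT is exploratory in the SAP.** This stands, and it limits the point: per protocol for CT rests on the protocol sentence alone. If the SAP is taken to supersede it, the CT analysis set is simply undefined, which also needs correcting.

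**Per protocol was a deliberate choice.** The SAP names the bias, protects the confirmatory outcome and gives a mechanistic reason for the rest. A per-protocol CT analysis has a place. As the only planned one, it still selects on an event that treatment may change.

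**A reader might infer more than the documents support:**

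- *That every early-discharged patient is certainly dropped.* Route (a) alone spares discharge after about 90 h, and route (b) depends on how a section title is read.
- *That the 75% denominator alone decides the matter.* Route (b) operates whatever the denominator is.
- *That the per-protocol rule causes 4.2 to 9.5 points of bias against the drug.* Those figures use assumed rates and include scans that would be declined under any rule. Sicker exclusions could also cancel them.

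**Conclusion.** The point holds as a weakness in the analysis of one secondary (in the SAP, exploratory) outcome. The protocol assigns day-5 CT complications to per protocol, at least two readings of that set remove patients who are offered the scan, and nothing in either document analyses all scans. This sits poorly with the SAP's own argument for intention to treat on the primary outcome.

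Size and direction are unknown. On the assumed rates, using all scans removes 2.4 to 5.8 points at 50% uptake and 3.5 to 8.2 at 80%, always less than one standard error of a comparison with at most 45 per arm. The conclusion rests on early discharge differing between arms and on early-discharged patients having fewer complications. The first the SAP allows for; the second fits its expectation that early discharge mostly means recovery.

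The confirmatory result, PASS at 48 h by intention to treat, is not affected. The change is worth making because it is cheap, not because the trial's conclusion depends on it.

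**What to change.** State in SAP 2.5, and align Protocol 9.3: *The main analysis of day-5 CT outcomes includes all treated patients with a day-5 scan, in the arm to which they were randomized; the per-protocol analysis is supportive.*

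Also:

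- Define the denominator of the 75% rule.
- Say whether early discharge is a major protocol deviation.
- Report by arm the early discharges, the other reasons for per-protocol exclusion, and the outpatient scans offered and declined.
- Preferably apply the same as-randomized rule to length of admission, 90-day mortality and Atlanta severity. SAP 2.2 lists these as secondary, so they fall under per protocol, although SAP 5 takes them from medical records or files.

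**Cost.** No new procedure or scan is needed. The main CT comparison would include patients with shorter exposure. Declined scans stay missing, as do patients with under 48 h of treatment, whose data collection stops, so bias is reduced and not removed. A change to Protocol 9.3 may need an amendment approved by the ethics committee and the medicines agency (Protocol 11). It should be made before unblinding, the limit that Protocol 9.3.2 already sets for missing-data handling.

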#### 9.3.1. Criteria for the termination of the trial

The trial is terminated when full datasets for 90 patients with AP has been collected.

#### 9.3.2. Missing data

Handling of missing data will be defined in the final statistical analysis plan and finalized before unblinding of data.

#### 9.3.3. Deviations from the original statistical plan

It will be reported if any deviations from the original statistical plan occur.

## 10. Methods: monitoring

### 10.1. GCP monitor

A monitor will be allocated from the good clinical practice (GCP) unit at Aarhus and Aalborg University Hospitals, and an agreement between Aalborg University Hospital and the GCP unit will be signed. The responsible monitor will contact and visit the principal investigator on a regular basis. The monitor will be authorized to inspect the different study records (CRFs, source data/documents and other relevant data), provided that the subjects' information is kept confidential in accordance with the data protection agency

conditions. It will be the responsibility of the monitor to inspect CRFs regularly throughout the study to ensure compliance and completion of the protocol and that consistent and accurate data is entered in these. Monitor will check and verify that each subject has given written informed consent for direct access to study records as well as study procedures. Principal investigator (or his/her representative) agrees to cooperate with the monitor to ensure that all potential problems, discovered during the monitor's visit, will be solved. Investigator provides direct access to source data/documents (including medical records) during monitoring, auditing and/or inspection by the Danish Medicines Agency or The Danish Data Protection Agency.

## 10.2. Assessment of safety and harms

### 10.2.1. Adverse event and adverse reaction

An adverse event (AE) is according to the ICH-guideline defined as "any untoward medical occurrence in a patient administered a medicinal product and which does not necessarily have to have a causal relationship with this treatment" and can be expected as well as unexpected. An adverse reaction (AR) concerns noxious and unintended responses to a medical product, meaning that a causal relationship between a medical product and an AE is at least a reasonable possibility. As these patients are acutely ill and admitted to hospital during participation in the study, they are expected to have certain symptoms and laboratory result deviations frequently associated with the disease. These are listed below:

Symptoms	Laboratory result deviations
abdominal pain	elevated plasma amylase or lipase
nausea	elevated plasma CRP
vomiting	elevated serum creatinine
	elevated serum liver enzymes and/or bile acids
	elevated blood sugar levels
	elevated white blood cell count

These will not be reported as AE's as well as AE's assessed clinically insignificant will not be reported. The evaluation hereof will fall upon study-affiliated doctors assessing the individual patient under the responsibility of the primary investigator. AE's and AR's will be registered for 45 hours after the study medication is discontinued. This corresponds five times the half-life of Methylnaltrexone (Relistor®) which is 8-9 hours (32). Any AE or AR fulfilling the criteria for serious (SAE/SAR) will be reported according to the descriptions below. All expected and un-expected AEs and ARs to be reported, will be registered in the CRF and included in a final report which will be registered into EudraCT along with the results at the trial's termination. Information about AEs will be collected from the first administration of any investigational product until the end of the study.

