### 6.3. Trial design

This study is an investigator-initiated, double-blind, placebo-controlled, parallel-group of fixed methylnaltrexone dose conducted at four referral centers for pancreatitis in Denmark. A group of **90 patients with AP** will be prospectively included and randomized to receive intravenous methylnaltrexone or matching placebo in a 1:1 ratio. Patients will be treated for 5 days during hospital admission.

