## 7.5. Participant timeline

### 7.5.1. Study days

A detailed description of the study procedures is illustrated in Table 1. Patients will be evaluated daily during admission by medical personnel and treated in agreement with the IAP/APA evidence-based guidelines for the management of AP (2). As part of the study, they will receive daily infusions with methylnaltrexone or matching placebo, and have the following examinations performed: i) clinical outcome and patient symptoms will be evaluated by means of both well-validated questionnaires and information from the patient's medical records (see section 9.1.2.), ii) the PASS score will be obtained daily and used to document the primary endpoint 48 hours after randomization, iii) blood samples (including C-Reactive Protein (CRP), interleukin (IL)-6, IL-8, IL-18, tumor necrosis factor alpha (TNF- $\alpha$ ) and cluster of differentiation 163 (CD163)) will be drawn

daily with the purpose of evaluating the systemic inflammatory response, and iv) an abdominal contrast-enhanced CT study will be performed at inclusion and after conclusion of treatment at day 5 (+/- 1 day) to document the presence and extent of pancreatic inflammation, fluid collections and necrosis according to the definitions given in the revised Atlanta criteria (20). As an integrated part of the CT exam at day 5 (+/- 1 day) patients will undergo assessment of the colon/gut transit time using radiopaque markers given orally in the morning on day 3 up to the planned CT exam. Finally, the intestinal permeability will be evaluated by a polyethylene glycol (PEG) 400/4000 test (see section 9.1.5.) 48 hours after randomization. At hospital discharge, patients are invited for a follow-up visit on day 14 (+/- 2 days) after randomization where the outcomes assessed during hospital admission (blood test and questionnaires including the PASS score) will be reassessed. Patients ready for discharge prior to completing five days treatment with methylnaltrexone will be handled according to the following:

- < 48 h of treatment: All data collection will be terminated upon discontinuation of the study medication and participant is regarded as dropout.

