6.3. Major Protocol Deviations

It is expected that a proportion of the patients included into the study, will recover before 5 days have passed and thus be discharged before completing the study protocol. In case of early discharge, data handling of both primary and secondary outcomes be stratified according to table 2:

< 48 hours of treatment	All data collection will be terminated upon discontinuation participant is regarded as dropout.
\geq 48 hours of treatment, but discharge before day 5	Participant will be lost to follow-up on the following outcomes: daily PASS scores, blood samples, vital signs. The participant will be asked to complete questionnaires at home, and they will be offered a follow-up CT scan in an outpatient setting on day 5 (+/- 1 day). Furthermore, they will be invited to participate in the 14-day follow-up and mortality will be registered retrospectively.

Table 2

For the statistical analyses, the Last-Observation-Carried-Forward method will be employed in case of early hospital discharge or other reasons for missing values. We expect most missing values to be a consequence of early discharge (~ recovering early from their disease) and thus the Last-Observation-Carried-Forward method will reflect this by carrying forward a value corresponding to low disease activity after discharge, which we find to be a fair assumption. If this is not the case, e.g. if a lot of missing values are due to severe disease, we will consider using other methods for imputation of missing values.

7. Implementation of Analysis Plan

A monitor will be allocated from the good clinical practice (GCP) unit at Aarhus and Aalborg University Hospitals, and the responsible monitor will contact and visit the principal investigator on a regular basis. The monitor will be authorized to inspect the different study records (CRFs,

Aalborg, Denmark

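### Protocol section 10.2.1 gives two incompatible end points for adverse-event collection, and the rule for discharge before 48 h of treatment adds a third

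*Protocol*

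**What the plan says.** Protocol section 10.2.1 contains two statements on how long AEs are collected:

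- First rule: "AE's and AR's will be registered for 45 hours after the study medication is discontinued". The reason given is pharmacokinetic: "This corresponds five times the half-life of Methylnaltrexone (Relistor®) which is 8-9 hours".
- Second rule, at the end of the same section: "Information about AEs will be collected from the first administration of any investigational product until the end of the study".

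Neither sentence is limited to a class of event, and nothing says which takes precedence. The end of the study is not defined for AE purposes. Table 1 in section 7.5.1 places that label over the 120 h column and has a separate follow-up column for day 14. Section 5 uses last subject, last visit as the conclusion of the trial.

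A third rule is in section 7.5.1, under the introduction "Patients ready for discharge prior to completing five days treatment with methylnaltrexone will be handled according to the following". For those with under 48 h of treatment: "All data collection will be terminated upon discontinuation of the study medication and participant is regarded as dropout". SAP section 6.3, Table 2, repeats it for early discharge: "All data collection will be terminated upon discontinuation participant is regarded as dropout".

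Other safety text bears on the same patients:

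- Section 8.2 has discontinuing subjects asked about adverse events, although they need not answer.
- Section 7.3.2 requires ongoing SAEs in withdrawn participants to be followed until they are resolved, chronic or stable.
- Section 10.2.3 requires SAEs and related AEs to be followed up. Participants with unresolved events get a safety visit one to two weeks after final examination or premature termination. The only exemption is for those who dropped out before randomization or before starting active treatment.

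**The concern.** An AE count can be interpreted only if the period of observation is known. Here that period depends on which sentence of section 10.2.1 is followed, and under two of the three rules it also depends on when the patient's treatment stops. Stopping is a post-randomization event. SAP section 2.5 allows that it may differ by arm, through earlier discharge or discontinuation for side effects on methylnaltrexone. If it does, the arms would be observed for different lengths of time.

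What is at stake is the safety record that section 10.2.1 sends to the final report and to EudraCT. Neither the sample size nor the PASS analysis depends on it. The SAP does not resolve the conflict, because the available text has no AE endpoint, AE window or AE analysis.

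**Working it through.** **The protocol's own figure.** Five half-lives of 8 to 9 h give 5 × 8 = 40 h to 5 × 9 = 45 h. The stated 45 h is reproduced at the upper half-life.

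**Inputs.**

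- Treatment duration is 120 h, from Protocol section 6.3: "Patients will be treated for 5 days during hospital admission".
- Table 1 puts its End of study column at 120 ± 2 h.
- The late visit is described in section 7.5.1: "patients are invited for a follow-up visit on day 14 (+/- 2 days) after randomization". That is 14 × 24 = 336 h, with a range of 12 × 24 = 288 h to 16 × 24 = 384 h.
- Assumption: the infusion starts at randomization, so all times share one clock.

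**Formulas.** With drug stop at time s, in hours:

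- first rule: window closes at s + 45;
- second rule: window closes at 120 (Table 1 label) or 336 (day 14);
- early-discharge rule (s < 48 only): window closes at s.

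| Drug stops at | First rule | Second rule, Table 1 label | Second rule, day 14 | Early-discharge rule | Day 14 ÷ first rule |
|---|---|---|---|---|---|
| 24 h | 69 h | 120 h | 336 h | 24 h | 336/69 = 4.9 |
| 72 h | 117 h | 120 h | 336 h | not applicable | 336/117 = 2.9 |
| 120 h | 165 h | 120 h | 336 h | not applicable | 336/165 = 2.0 |

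**Can the two rules in section 10.2.1 agree?**

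- Under the Table 1 label they agree only if s + 45 = 120, so s = 75 h.
- Under day 14 they agree only if s = 336 − 45 = 291 h, well beyond the five-day course.
- Last subject, last visit is a calendar date for the whole trial and gives each patient a different window.

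For a five-day completer none of the three readings gives 165 h.

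**Sensitivity to the start time.** If the infusion starts d hours after randomization, the first rule closes at 165 + d for a completer. Reaching even the earliest day-14 visit would need d = 288 − 165 = 123 h, so a short delay does not remove the conflict.

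**What this could do to counts.** The documents give no AE rate. Assume a constant 0.1 events per patient-day, for illustration only. Expected events for a completer are then:

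- 120 h: 0.1 × 120/24 = 0.50
- 165 h: 0.1 × 165/24 = 0.69
- 336 h: 0.1 × 336/24 = 1.40

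At 0.05 per day these become 0.25, 0.34 and 0.70. At 0.2 per day they become 1.00, 1.38 and 2.80. The ratios do not change.

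**The under-48 h group.** For a patient discharged after 24 h of treatment, post-drug AE observation is 0 h under the early-discharge rule, 45 h under the first rule, and 336 − 24 = 312 h if the second rule means day 14.

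**The case against.** Several points on the other side are sound.

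- **Scope of the third rule.** A reader might infer that all data stop whenever the drug stops, including for patients who stop because of side effects. The text does not say that. Section 7.5.1 and SAP section 6.3 both introduce the rule for early discharge. SAP section 3.2 does define a dropout as anyone treated for under 48 h, without mentioning discharge, so wider use is conceivable, but it is not stated.
- **Remaining safety follow-up.** Sections 7.3.2, 8.2 and 10.2.3 keep part of the safety net for those who discontinue, so a known event is not abandoned. These sections govern questioning at discontinuation and follow-up of events already identified. They set no window for new events and so do not settle the conflict.
- **The larger ratio.** Setting 336 h against 120 h gives 2.8, but that compares two readings of one sentence. The gap between the two rules for a completer, with the second read as day 14, is 2.0-fold. The 120 h reading rests only on a table heading.
- **Bias between arms.** The unclear wording applies to both blinded arms alike, and the SAP plans no between-arm AE test. Differences between sites would need sites to apply different rules, and one GCP unit checks the CRFs for consistency. These points stand against any claim of demonstrated bias. They do not rule it out, because blinding cannot equalize a window tied to stopping time if treatment affects that time.
- **Reading the sentences together.** One could suppose that the 45 h limit is for non-serious events and the longer one for serious events, or that each patient's study ends 45 h after the last dose. No section says either.

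**Conclusion.** The inconsistency is real and should be corrected before the AE data are summarized. For a five-day completer, section 10.2.1 closes AE collection at 165 h by one sentence and at 120 h or 336 h by the other. The first rule and day 14 differ 2.0-fold, and the gap is wider for patients who stop sooner. For patients ready for discharge before 48 h of treatment, the instruction to end all data collection contradicts the 45 h window and sits badly with the safety follow-up text.

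The consequence is that AE observation time may differ between patients. It may differ between arms only if stopping or discharge times do, which SAP section 2.5 allows for but does not establish. A reader might conclude that the safety comparison is already biased or unusable. The documents do not support that: they give no AE rate and no stopping times by arm, and they do not show which window was intended.

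The hours assume that treatment starts at randomization and lasts 120 h. The conclusion that the rules conflict does not depend on the illustrative AE rate.

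**What to change.** Three wording changes would settle it:

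1. In section 10.2.1, replace the two statements with one AE window that applies to every treated participant.
2. Define the end of the study for AE purposes, and make the Table 1 label and the undefined study phase in section 10.2.2 agree with that definition.
3. In section 7.5.1 and in SAP section 6.3, Table 2, state that ending data collection for discharge before 48 h of treatment does not apply to AEs and SAEs. Cross-refer to sections 7.3.2, 8.2 and 10.2.3.

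The sponsor chooses the window. Ending 45 h after the last dose has a stated five-half-life rationale. Day 14 uses a visit already planned for most patients and gives nearly equal calendar observation whatever the stopping time. If day 14 is chosen, events up to 45 h after the last dose can still be flagged separately in the tables.

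The cost is amended wording in both documents and a little more AE recording. Patients discharged before 48 h may need one added contact, because the early-discharge rules repeat the day-14 invitation only for those with at least 48 h of treatment.
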